1.36 DATA FLOW DIAGRAM

The above diagram and style was interpreted from an initial data flow diagram created and provided by [name] at the University of Bristol. It has been repurposed and amended by University of Leicester to illustrate data flows specific to the BCIS-4 project.

Figure 4 Data Flow Diagram

1.37 DATA COLLECTION TOOLS AND SOURCE DOCUMENT IDENTIFICATION

NHS Digital will be used as the primary data source to ascertain the primary and secondary outcomes after hospital discharge. Permission will be sought from all participants to access centrally held NHS records and the Office for National Statistics (ONS) as part of the eligibility process. This will also allow for collection and confirmation of clinical events as well as participant deaths where consent remains. Consent for NHS number, date of birth, and sex to be used in order to obtain data linkage for NHS Digital will be specifically requested. Data extracts will be received by the LCTU, UoL and stored in the Research Filestore (RFS). This data will be archived and destroyed in line with agreements with NHS Digital and equivalent services.

Other source data documents will be hospital and primary care health records, and, as data will be entered into Healthbit® directly, the mobile application will also be considered as source data. Healthbit® will be designed to ensure that it collects data adequately, and audit trails will be available to demonstrate validity both during and after the trial. Where sites prefer, paper CRFs will also be provided as a data recording tool, although sites will be encouraged to enter data directly onto ResearchApp™ (Healthbit®). Where this option is utilised, data collected on paper CRFs outside of that sitting in patient records will also be considered as source data.

Baseline and follow-up data on quality of life surveys can be completed by participants using the mobile app ResearchApp™ (Healthbit®); attendance at GP Practice or hospitalisation following discharge can also be self-reported by participants on the same mobile app. Participants will receive reminders prompting them to complete the surveys at 4 weeks post-operation and at the relevant timepoints for the follow-ups if not already completed. Where a participant is unable to complete the surveys electronically, a designated research team member will arrange either a face-to-face, telephone, or video interview with the participant pre-operatively and at 6 weeks post-operation, coinciding with participant's pre-operative consent and post-operative clinic follow-up if appropriate. This process will continue for all required follow-ups required as part of the trial. All data collection will be undertaken locally and pseudonymised results reviewed centrally using the related platform Healthbit IQ™ (Healthbit®).

All data collected for the PROM and Quality of Life assessments will be via standardised and validated questionnaires. Data collected for purposes of Health Economic analysis will be collected on bespoke designed questionnaires, designed by the Health Economist. To maximise completeness of data, researcher staff can complete these with the participant and enter this data on their behalf, for

example in the event of technical difficulties using ResearchApp™ (Healthbit®), and this can be done remotely to reduced participant burden.

All personal data will be stored for up to 3 years after the end of the trial to ensure participants can be contacted by research staff at sites in the instance where the participant has provided consent to receive the results of the trial. After this, only select electronic pseudonymised data will be stored on the UoL RFS for use in potential future ethically approved research. Where consent has been provided for future research, signed ICFs along with the select data will be kept indefinitely as evidence of this and to support any of this potential research. The PIS and ICF will comply with this.

1.38 DATA STORAGE

The primary trial database is provided by ResearchApp™ (Healthbit®, London UK). This is a flexible modular, data capture and storage platform that combines Investigator and Participant user-friendly mobile apps (iOS and Android) for bedside and remote data capture by research staff and participants, with built in quality assurance tools that promote efficient data capture. ResearchApp™ (Healthbit®) is also multilingual, facilitating remote data capture from diverse communities (33).

Trial data collected via ResearchApp™ and Healthbit IQ™ and stored on MS Azure Cloud will be transferred securely via Healthbit's® Application Programme Interface (API) and stored on secure servers (e.g., RFS) hosted by the LCTU, UoL, throughout the duration of the trial and up to 6 years after the trial is complete in the UK at UoL, in accordance with General Data Protection Regulation (GDPR) and Information Assurance Services (IAS) standards. Data transferred to Sweden as part of the SWEDEHEART co-ordination will be stored for 25 years in line with the country's legal requirements. All data entered into the eCRF and any process derived from the eCRF (source data verification, adverse event reporting) will be pseudonymised. Participants will therefore be solely identified by their participant ID, which is assigned in the randomisation system, Sealed Envelope. Pseudonymised source data will be made available to the Executive Committee (EC) (see section 1.54) and/or LCTU Coordinating Centre for SAE reporting.

Local site files will be archived by sites as per local requirements or for 6 years after publication of the trial.

Participants will be asked to consent to the sharing of pseudonymised medical data with the Coordinating Centre in Sweden, that their medical records may be inspected for purposes of monitoring, that their medical data relevant to this trial will be stored and analysed while maintaining

confidentiality in accordance with local data protection laws, and may be subject to audits by authorised representatives of the Coordinating Centre or the Sponsor.

Consent will be sought for life-long trial follow-up beyond the scope of the follow-up schedule currently planned in this protocol using HES / ONS.

1.39 DATA PROTECTION

Participants' personal data shall be treated in confidence and in compliance with International Committee on Harmonisation of Good Clinical Practice (ICH-GCP), the UK Policy Framework for Health and Social Care and the UK GDPR. When processing or archiving personal data, the Sponsor or its representative shall take all appropriate measures to safeguard and prevent access to this data by any unauthorised third party.

The CI will have access to the trial documentation and will be the data custodian for the BCIS-4 UK arm of the trial.

Each participant will be assigned a unique identification number upon randomisation. All personalised information for participants will be kept confidentially at the recruiting site unless there is a specific need for transfer of a copy of a participant consent form to another site for trial-related purposes, i.e., proof of consent where a site different to that of the consenting site is performing the PCI or CABG.

All electronic patient identifiable information will be held on a secure, password-protected database accessible only to essential personnel. Each person (both the field-based data collectors and LCTU) will be assigned access to only the portions of the database they need. Access is provided under "hard" password protection that are changed at 6-month intervals. All data are encrypted. The required dataset for receipt by the SWEDEHEART team for consortium analysis will be defined and transferred securely via Healthbit's® Application Programme Interface (API). Depending on the required data items, this may mean that whole surveys (forms) may be transferred, however this data will always be pseudonymised at point of transfer and receipt.

Paper documentation will be stored in a locked filing cabinet in the relevant research office. Neither hard copies nor electronic files containing personal information will be removed from the research office or stored in a non-secure manner electronically. The study research team will comply with local NHS Trust data protection policies. Direct access to source data/documents may be required for trial-related monitoring.

1.40 ACCESS TO DATA

Direct access will be granted to authorised representatives from the Sponsor, host institution and the regulatory authorities to permit trial-related monitoring, audits and inspections in line with participant consent.

1.41 DATA SHARING WITH THE INTERNATIONAL STICH-3 CONSORTIUM

Participants of STICH3-BCIS4 will be asked to provide a specific informed consent for their data to be included in the STICH-3 analysis described in this protocol at the time of providing their consent to the UK trial. A national PIS and ICF will contain clear wording that allows pseudo-anonymised data to leave each country and to be received by the SWEDEHEART team. The ICF will also explain that for verification of data, authorised representatives of the Sponsor, as well as any relevant authorities, may require access to parts of medical or trial records that are relevant to the trial, including the participant's medical history.

1.42 ARCHIVING

All paper data will be retained for 6 years after completion of the trial, in accordance with UoL SOPs. The data will be stored at a UoL approved archiving facility which will ensure that it is stored securely and accessed only by authorised individuals. Sites will be required to archive their own paper data in line with their local Trust SOPs.

Electronic data will be transferred securely and stored on secure servers hosted by the LCTU (e.g., RFS), UoL, throughout the duration of the trial, and 6 years after the study is complete, in accordance with GDPR and IAS standards. Healthbit® will retain data whilst the LCTU, UoL utilises its platform for the duration of the trial and for the agreed retention period. Once LCTU, UoL requests all records to be deleted, data will be removed from the back-ups within 3 months.

As above, research data containing personal data will be stored for up to 6 years, with signed ICFs being kept indefinitely. Storage will comply with the University of Leicester archiving Standard Operating Procedure. Details can be found at: <http://www2.le.ac.uk/office/ias>.

STATISTICAL ANALYSIS

Researchers at the LCTU will perform the trial statistical analyses for BCIS-4. A detailed SAP will be finalised before any analysis of the data by treatment group is undertaken.

1.43 ANALYSIS POPULATION

The primary analysis will be based on ITT principles with the analysis population consisting of all participants who are randomised and compared in the groups to which they were allocated regardless of treatment being received. The per-protocol (PP) population will consist of all participants who underwent revascularisation as randomised, excluding patients who had a major protocol deviation e.g., patients who crossed over, had their allocated treatment changed or discontinued by the treating physician at any time, or withdrew consent.

1.44 BASELINE CHARACTERISTICS

The baseline characteristics of the patients will be summarised by group. Continuous variables will be summarised by mean and standard deviation, or median and inter-quartile range if data do not have a symmetric distribution. Categorical variables will be summarised with counts and percentages. No statistical comparisons of participant characteristics at baseline will be performed between groups.

1.45 INTERNAL PILOT

Key assumptions about recruitment, inclusivity, and adherence will be tested in an internal pilot with pre-specified stop / go criteria at 12 months. The primary progression criteria will be recruitment; target 0.7 pts/site/month with 1.5 new sites set up per month to 18 sites within 12 months of green light. Using the thresholds of 100% and 75% of these targets, we can specify the following traffic light system: Green: Proceed, Amber: Amend, consult and Red: Discuss with funder, as shown below. The TSC in consultation with the funder will determine progression. As contingency, recruitment in the range 0.5 pts/site/month would require an increase in the number of centres to 35 to achieve the recruitment target within 48 months. The internal pilot will be used to refine and amend recruitment strategies where needed, to ensure the sample is representative of the UK population.

Table 2 Red, Amber, Green Progression Criteria

Progression criteria	Red	Amber	Green
	≤74%	75-99%	100%
1. Recruitment rate (n/site/month)	<0.53	≥0.53 - <0.7	≥0.7
2. Number of sites opened	<13	13-17	≥18
Total number of participants recruited (12 m pilot)	42	43-81	82

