PI	Principal Investigator
PIS	Participant Information Sheet
POC	Polygon of Confluence
POT	Proximal Optimisation Technique Procedure
PP	Per Protocol
PPI&E	Patient and Public Involvement and Engagement
PROMS	Patient Reported Outcome Measures
QALYs	Quality-Adjusted Life Years
RCT	Randomised Controlled Trial
R&D	Research and Development
REB	Research Ethics Board

REC	Research Ethics Committee
RFS	Research Filestore
RGO	Research Governance Office
R&I	Research and Innovation
SAE	Serious Adverse Event
SAP	Statistical Analysis Plan
SAQ-7	Seattle Angina Questionnaire-7
SGLT2	Sodium-Glucose Co-Transporter-2 Inhibitors
SIV	Site Initiation Visit
SOP	Standard Operating Procedures
STEMI	ST Elevation Myocardial Infarction
STICH-1	Surgical Treatment for Ischemic Heart Failure Trial
STICH-3	The Canadian CABG or PCI in Patients with Ischaemic Cardiomyopathy Trial
STICH3-BCIS4	A multi-centre randomised trial of surgical versus percutaneous revascularisation of ischaemic left ventricular dysfunction in the United Kingdom, with embedded internal pilot and health economic analysis
SWEDEHEART	The Swedish Web-system for Enhancement and Development of Evidence-based care in Heart disease Evaluated According to Recommended Therapies
SYNTAX SCORE	Synergy Between PCI With Taxus and Cardiac Surgery
TSC	Trial Steering Committee
TMF	Trial Master File
UK	United Kingdom
UKCRC	The UK Clinical Research Collaboration
UoL	University of Leicester
VA ECMO	Venoarterial Extra Corporeal Membrane Oxygenation

KEY WORDS

Ischaemic left ventricular dysfunction, revascularisation, coronary artery bypass grafts, percutaneous coronary intervention.

STUDY SUMMARY

Study Title	A multicentre randomised trial of surgical versus percutaneous revascularisation of ischaemic left ventricular dysfunction (iLVSD) in the United Kingdom, with embedded internal pilot and health economic analysis
Internal ref. no (or short title)	CABG or PCI in Patients with Ischaemic Left Ventricular Dysfunction (STICH3-BCIS4)
Study Design	
Multicentre, open label, parallel group, RCT of two common revascularisation strategies in people with iLVSD.
 
An internal pilot including built in progression criteria, to assess whether the target number of UK centres within 9 months of green light, and recruitment rate of one participant per site per month, can be achieved.
 
A health economic evaluation will assess the cost-effectiveness of the intervention from an NHS and English societal perspective.

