Recruitment Period	41 months with a built in 9-month internal pilot (based on 0.7 participants per site per month). As a contingency, slower recruitment at 0.5 participants per site per month would require 35 sites and 48 months to complete recruitment.
Analysis	
The primary analysis of the primary outcome will be performed in the intention to treat population using survival analysis methods and compare groups using a log-rank test calculating the hazard ratio with a cox regression model. All analysis methods will be pre-specified fully in the statistical analysis plan before data lock.
 
Health Economic Evaluation will determine the cost-effectiveness of CABG, compared with PCI, from the perspectives of the UK, NHS, personal social services, and the wider societal perspective. We will conduct the evaluation alongside the clinical trial over a minimum 4-year time horizon and a model-based evaluation over a lifetime horizon.
 
The trial data will be shared with International STICH3 consortium for an individual patient data analysis of multiple similar trials that will test whether CABG is superior to PCI for the outcome All-cause Mortality at 5 years.

ROLE OF TRIAL SPONSOR AND FUNDER

The trial has been funded by a grant from the National Institute for Health and Care Research Health Technology Assessment (NIHR HTA) Programme (ref: NIHR155123). Additional support and resources for the trial will be provided by the participating Trusts and their corresponding Clinical Research Networks (CRN). The funder will be responsible for funding the trial but will not be part of the trial conduct, data analysis and interpretation, manuscript writing, and dissemination of results.

The Sponsor, the University of Leicester, will be responsible for all aspects of the trial. The University of Leicester is registered as a research Sponsor with the Department of Health and routinely takes responsibility as Sponsor for research activities within the NHS. The Sponsor will delegate duties to other parties, including Leicester Clinical Trials Unit (LCTU), this delegation will be formally documented. However, like the funder, the Sponsor will not be part of the trial conduct, data analysis and interpretation, manuscript writing, and dissemination of results.

TRIAL FLOW CHART

[figure not shown]

Figure 1 Trial Flow Chart

TITLE

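### The internal pilot's progression figures disagree: the total-recruits row in Table 2 does not fit its percentage headers, and the Study Summary gives a different rate and duration

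*Protocol*

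**What the plan says.** Section 1.45 describes "pre-specified stop / go criteria at 12 months". The target is "target 0.7 pts/site/month with 1.5 new sites set up per month to 18 sites within 12 months of green light". Cut-offs follow: "Using the thresholds of 100% and 75% of these targets, we can specify the following traffic light system".

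Table 2 applies one set of column headers (red at 74% or less, amber 75-99%, green 100%) to three rows:

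| Row | Red | Amber | Green |
|---|---|---|---|
| 1. Rate per site per month | below 0.53 | 0.53 to below 0.7 | 0.7 or more |
| 2. Sites opened | below 13 | 13-17 | 18 or more |
| Total recruited in 12 months (unnumbered) | 42 | 43-81 | 82 |

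The Study Summary describes the pilot differently in two places. Its Study Design row says the pilot is "to assess whether the target number of UK centres within 9 months of green light" can be reached, together with a "recruitment rate of one participant per site per month, can be achieved". Its Recruitment Period row gives a nine-month pilot based on 0.7. The summary's Research Question/Aims row and section 1.9 both put the pilot assessment at 12 months, and section 1.23 plans the whole trial on 0.7.

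**The concern.** The pilot criteria are the protocol's only numeric progression rule; section 1.48 plans no formal efficacy interim analysis and no statistical rule for early termination. A rule of this kind is useful only if the same recruitment data give the same answer to everyone who reads it.

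Two things prevent that. The total row carries percentages that its numbers do not meet, so a pilot can be red on a numbered criterion and amber on the total. And the summary's pilot has a different rate and length from the one in section 1.45. If this is left open until pilot data arrive, the choice of figure could be made after recruitment is known.

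**Working it through.** **Inputs.** From sections 1.23 and 1.45: 1.5 new sites per month, 18 sites at month 12, at least 28 sites in all, 0.7 participants per site per month, 630 participants in 41 months. From Table 2: 42, 43-81 and 82. From the Study Summary: 1.0 per site per month, and nine months.

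**1. Reproduce the plan's own figures.** Count each month's new sites as active from the start of that month.
- Site-months to month 12: 1.5 × (1 + 2 + … + 12) = 1.5 × 78 = 117. Recruits: 117 × 0.7 = 81.9, which gives the stated 82.
- Site-months to month 41, capped at 28 sites: 1.5 × (1 + … + 18) + 23 × 28 = 256.5 + 644 = 900.5. Recruits: 900.5 × 0.7 = 630.35, which gives the stated 630.

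Mid-month opening would give 75.6 at month 12 and end-of-month opening 69.3, so start-of-month counting is the convention that matches.

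**2. Compare the total row with its headers.**
- 42/82 = 51.2% and 43/82 = 52.4%.
- 0.75 × 82 = 61.5, and 61/82 = 74.4%.
- Totals of 43 to 61 therefore lie at 52-74% of target but are printed under the 75-99% header.

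**3. Compare the total row with the numbered rows**, with sites opening evenly over 12 months.
- 18 sites at 0.52: 117 × 0.52 = 60.8, about 61. Rate red, total amber.
- 12 sites at 0.7: 78 × 0.7 = 54.6, about 55. Sites red, total amber.

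**4. A likely origin of 42.** With 12 sites (just below the amber edge) at 0.53, 78 × 0.53 = 41.3. The figure looks like both criteria at the red edge together, which is a product of the two rather than 75% of the total.

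**5. What the product gives at the amber edge.**
- Exact 75% on both criteria: 0.75 × 0.75 × 81.9 = 46.1, which is 56% of target.
- The table's own edges, 13 sites at 0.53: (13/12) × 78 × 0.53 = 84.5 × 0.53 = 44.8, about 45.

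**6. What a separate 75% cut-off on the total would do.** It would read 61 or fewer, 62-81, 82 or more.
- 14 sites at 0.53: (14/12) × 78 × 0.53 = 91 × 0.53 = 48.2.
- 16 sites at 0.58: (16/12) × 78 × 0.58 = 104 × 0.58 = 60.3.

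Both are amber on rate and on sites, yet both would be red on the total.

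**7. Set the summary beside the rest.**

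| Place | Rate | Time |
|---|---|---|
| Summary, Study Design | 1.0 | 9 months (for opening centres) |
| Summary, Recruitment Period | 0.7 | 9-month pilot |
| Summary, Research Question/Aims | not given | 12 months |
| Section 1.9 | not given | 12 months |
| Section 1.23 | 0.7 | not given for the pilot |
| Section 1.45 | 0.7 | 12 months |

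At 1.0 the same site schedule would give 117 recruits at month 12 and 900.5 at month 41, against the stated 82 and 630. Of the two rates, only 0.7 fits the plan. A trial exactly on plan reaches 0.7/1.0 = 70% of the Study Design rate.

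**The case against.** The strongest reply is that the total row was never a criterion. The 75% rule in section 1.45 refers to the rate and site targets, only those two rows are numbered, and 42 is close to both failing together. On that view the fault is a label. This is probably how the number arose, and it argues against treating 62 as the one right cut-off: step 6 shows that a 75% total overrides pilots that are amber on both numbered criteria. It does not rescue the row as printed, because nothing marks it as derived and it stands under percentages that it does not meet.

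Four stronger readings are tempting, and the document does not support them.
- A reader might infer that an on-plan trial is red by the summary. The summary has no colour bands; that colour comes from applying section 1.45's rule to the summary's rate. The conflict in rate and duration needs no such step.
- A reader might infer that amber lets the trial run on at half its recruitment, or that red stops it. Amber calls for amendment and consultation, red for discussion with the funder, and the steering committee decides with the funder.
- A reader might count 13 sites in amber as another error, since 13/18 is 72%. But 75% of 18 is 13.5, so this is rounding to whole sites.
- A reader might object that the 0.5 contingency rate lies below the red line. A fallback for missed targets is coherent with a red band that means talking to the funder.

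**Conclusion.** The inconsistency stands in two parts. In Table 2, totals of 43 to 61 are amber by count while being 52-74% of target, and the row can disagree with the numbered criteria without any statement of which governs. In the Study Summary, the rate of one per site per month and the nine-month timing conflict with the rest of the protocol.

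The percentages in the total row rest only on Table 2's own figures. The cross-row examples and the recomputed edge of 45 or 46 assume even site opening, counted from the start of each month; that convention is inferred from its reproducing 82 and 630. The origin suggested for 42 is also an inference.

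This should be fixed, but it is not critical. It concerns the governance of a feasibility decision taken by the steering committee with the funder. It does not touch the efficacy analysis.

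**What to change.** 1. Use 12 months and 0.7 per site per month throughout, replacing the nine-month and one-per-site-per-month wording in the Study Design and Recruitment Period rows of the Study Summary.
2. State in section 1.45 that the two numbered criteria, rate and sites, set the colour.
3. Take the total row out from under the percentage headers and label it as the derived product of the two criteria. Recompute its lower edge: about 46 from 75% on both, or about 45 from 13 sites at 0.53.
4. If the sponsor prefers the total as a separate 75% criterion, it must read 61 or fewer, 62-81, 82 or more. The protocol should then acknowledge that this is stricter than the two numbered rows together.

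The cost is a few words in the summary and section 1.45 and a change to one table row. The pilot may become slightly harder to pass, and clearly harder under the alternative in item 4. The change should be made before pilot recruitment is judged.
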